## 7 TRIAL PARTICIPANT ASSESSMENTS

### 7.1 Trial Participant Assessment Table

Assessment	Compression Bandage Treatment				Pre Screening	Drug Loading dose	Ixekizumab + CBT / Placebo + CBT Study					
	Week 1	Week 2	Week 3	Week 4			Week 0	Week 2	Week 4	Week 6	Week 8	Week 10
Patient has completed 4 weeks of Unsuccessful Compression Therapy	✓	✓	✓	✓	✓							
Informed Consent					✓							
Medical Hx inc smoking Hx					✓							
Bloods (screening for TB,Hep B & C, HIV)					✓							
Concomitant Medications					✓							
Observations (Weight, BP, Temp)					✓							
Perinuclear Cellulitis (possible exclusion from trial if confirmed)					✓							
Ulcer Assessment + Bx + Swab					✓							
Photos both limbs					✓							
DLQI					✓							
Eligible for the Study												
Ulcer Assessment						✓	✓	✓	✓	✓	✓	✓
Smell / Exudate / Colour							✓	✓	✓	✓	✓	✓
Perinuclear Cellulitis (possible exclusion from study if confirmed)						✓	✓	✓	✓	✓	✓	✓
Photos both limbs						✓	✓	✓	✓	✓	✓	✓
Blood Sample												✓
Skin Bx (All Participants)												✓
Swabs									✓			✓
Collection of Exudate where applicable												
Compression Therapy						✓	✓	✓	✓	✓	✓	✓
Ixekizumab or Placebo S/C Injection						160mg	80mg	80mg	80mg	80mg	80mg	80mg
DLQI												✓
Adverse Events						✓	✓	✓	✓	✓	✓	✓

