Target sample size	28 patients
Primary outcome(s)	A 40% reduction in ulcer size after 12 weeks compared to the initial wound size.
Key secondary outcomes	
Drug related adverse events and serious adverse events at 12 weeks.
 
Percentage reduction in ulcer size at 12 weeks compared to the initial wound size.
 
Percentage patients with healed ulcers
 
Time to ulcer healing
 
Percentage and absolute reduction in Pain score (0-10)
 
Dermatology life Quality Index DLQI
 
Compliance with compression
 
Treatment-related reduction of IL17 levels in wound fluid and biopsies*
 
Wound-infiltrating macrophage phenotype change from M1 to M2*
 
Alterations in wound microbiome

Trial analyses timelines	
Interim Analysis: After the first 14 patients have completed the 12 weeks of Intervention
 
Final Analysis: After the full 28 patients have completed the 12 weeks of Intervention

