## 2.2 Objectives

To evaluate the safety and efficacy of Ixekizumab over placebo at 12 weeks in a randomized double blind trial on patients with chronic venous ulcers failing well conducted standard of care therapy.

The evaluation encompasses wound size reduction, pain reduction, quality of life improvement as well as biological measures of inflammation reduction.

Regarding safety, specific emphasis will be on infections and changes in microbiome.

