### **4.2 Accrual Numbers and Timelines**

It is anticipated it will take 9 months to complete target accrual of 28 participants. Duration for individual patients on study will be approximately 16 weeks this includes the inclusion criteria of 4 weeks of unsuccessful compression bandaging.

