### **4.3 Eligibility Criteria**

Patients (or a representative) must provide written, informed consent before any screening or study procedures occur.

Patients will be eligible if they meet all of the inclusion criteria and none of the exclusion criteria. Inclusion and exclusion criteria will be checked at prior to and at randomisation, and only those patients that still meet the criteria will be included. No exceptions, waivers or exemptions will be granted.

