## 8 DISCONTINUATION / WITHDRAWAL / TRANSFER

A Trial Participant may discontinue trial treatment for any of the following reasons:

- Intercurrent illness which prevents further treatment
- Withdrawal of consent for treatment by participant
- Any alterations in the participant's condition which justifies the discontinuation of treatment in the investigator's opinion
- Non-compliance with the compression bandaging
- Not attending the scheduled follow-up appointments

Discontinuation of treatment does not necessarily indicate withdrawal from the trial. The distinction between discontinuation of treatment and withdrawal from the trial is shown by the definitions in the following subsections.

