### **14.2 Adherence to Protocol**

Except for an emergency situation in which proper care for the protection, safety and well-being of the trial participant requires that an alternative treatment be used, the trial will be

conducted exactly as per the terms and instructions described in the approved protocol. No protocol exceptions, waivers or exemptions will be granted. If the protocol constraints cannot be met, then the participant will be treated off trial.

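### Sections 7.1 and 14.2 let randomised participants be removed from the study, against Sections 4.3 and 8, which can bias the week-12 responder comparison

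*Protocol*

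**What the plan says.** The table in Protocol 7.1 has two cellulitis rows. The first, "Perinuclear Cellulitis (possible exclusion from trial if confirmed", is ticked only at pre-screening and is an ordinary eligibility check. The second, "Perinuclear Cellulitis (possible exclusion from study if confirmed", stands below the line that declares the patient eligible. It has seven ticks, matching the seven injection visits (the loading dose and six later doses).

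Section 14.2, on adherence, states: "If the protocol constraints cannot be met, then the participant will be treated off trial". It does not limit this to the time before randomisation.

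Two other places point the other way. Section 4.3 says "Inclusion and exclusion criteria will be checked at prior to and at randomisation". Section 8 states that stopping treatment need not mean withdrawal, 8.1 allows follow-up to continue if the participant agrees, and 8.2 describes total withdrawal as the participant's own decision, after which nothing more is collected.

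On safety, Section 2.2 says "Regarding safety, specific emphasis will be on infections and changes in microbiome". The Trial Summary times the final analysis "After the full 28 patients have completed the 12 weeks of Intervention". Section 4.2 gives the accrual target as the same number: "It is anticipated it will take 9 months to complete target accrual of 28 participants". Section 6 also randomises 28.

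**The concern.** A site that confirms cellulitis at, say, week 6 has two instructions. The table suggests the participant may leave the study. Section 8.1 suggests that injections may stop while visits continue. Section 8 has no category for removal by the investigator, so the site cannot tell whether the week-12 ulcer measurement is still due.

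The trigger arises after randomisation. It is an infection, the type of event the safety objective singles out, so treatment may plausibly affect its frequency. It may also plausibly impede healing, and so be related to the primary endpoint (a 40% reduction in ulcer size at week 12). If removals differ between arms and fall mainly on non-responders, those who remain are no longer the groups that were randomised.

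A statistical analysis plan can define who is analysed. It cannot recover measurements that sites were allowed not to take.

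**Working it through.** **Plan's own figure.** The protocol gives no figure for exclusions, dropout or cellulitis. The power statement in 9.1 has no bearing on this point and is not used. All rates below are assumptions.

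**Step 1: the passages side by side.**
- Eligibility: 4.3 applies it before and at randomisation; the second row in 7.1 applies an exclusion at each injection visit after that.
- Stopping treatment: Section 8 keeps it apart from leaving the trial; the row in 7.1 and the sentence in 14.2 speak of leaving the study.
- Who decides: 8.2 leaves total withdrawal to the participant; 7.1 and 14.2 imply that the study team decides.

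**Step 2: removals from one arm.** Input from 9.1: 28 patients in two equal groups, so 14 per arm. Assumptions: true response 30% in both arms, and the k participants removed from one arm are all non-responders. Expected responders are 14 × 0.30 = 4.2, and the expected rate among those remaining is 4.2/(14 − k).

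| k removed | Expected rate | Spurious difference |
|---|---|---|
| 1 | 4.2/13 = 32.3% | 2.3 points |
| 2 | 4.2/12 = 35.0% | 5.0 points |
| 3 | 4.2/11 = 38.2% | 8.2 points |
| 4 | 4.2/10 = 42.0% | 12.0 points |

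The difference favours whichever arm loses the non-responders. If two are removed from each arm, both rates become 35.0% and the difference is zero.

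**Step 3: removals from both arms at unequal rates.** Same 30% true response; every cellulitis case is assumed to be a non-responder and removed; the remaining rate is 0.30/(1 − c), where c is the cellulitis rate.
- 10% against 0%: 33.3% against 30.0%, 3.3 points.
- 20% against 5%: 37.5% against 31.6%, 5.9 points.
- 30% against 10%: 42.9% against 33.3%, 9.5 points.

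**Step 4: sensitivity of a test.** Invented counts, Fisher's exact test, two-sided. With 9/14 against 4/14, p = 0.128. Dropping one non-responder from the first arm (9/13) gives p = 0.057; dropping two (9/12) gives p = 0.047. At this size two removals can move a result across 0.05.

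**Step 5: the timing line.** If all of the 28 randomised must complete 12 weeks, the chance of that is (1 − d)^28 for an assumed independent loss rate d: 0.95^28 = 23.8% at 5% loss and 0.90^28 = 5.2% at 10%. Read literally, the condition would probably not be met, and no rule says what follows then.

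**The case against.** The strongest reply is that Section 8 is the governing text and 7.1 is only a row label that says exclusion is possible. Cellulitis also fits the treatment-discontinuation grounds in Section 8, such as intercurrent illness. This stands in part: exclusion is not automatic, and nothing says that 7.1 or 14.2 takes precedence over 8.1. Equally, nothing says that 8.1 takes precedence over them. The conflict remains for sites to settle case by case.

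Section 14.2 can also be read as concerning treatment only, since it does not mention data or analysis. That is fair, but the sentence can equally be read as leaving the trial, so it needs the same clarification.

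A reader might infer four stronger things that the documents do not support.
- **That the final analysis is restricted to completers.** The line in the Trial Summary sets timing, not an analysis set, and can mean that the 28 randomised have reached week 12. The analysis set and missing-data rule may properly stand in an analysis plan not seen here.
- **That the infection signal is hidden.** Adverse events are ticked at the same visits as the cellulitis check, and 12.2.1 requires all of them to be recorded. The triggering event should therefore be captured. What can be lost is later infections, time at risk, and the later swab and ulcer data.
- **That participants who do not comply with compression are removed too.** Section 8 lists "Non-compliance with the compression bandaging" only as a reason to stop treatment.
- **That the result is biased in favour of ixekizumab.** No document gives cellulitis or exclusion rates by arm, and decisions would be made under blinding. Direction and size are open.

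**Conclusion.** The point holds as a contradiction with a bias risk. The on-treatment row in 7.1 and the sentence in 14.2 permit removal of randomised participants, in conflict with 4.3 and Section 8. The risk falls on the week-12 responder comparison and on infection, swab and ulcer data after the triggering event.

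The size is unknown. The range of about 2 to 12 points rests on three assumptions: 30% true response in both arms, one to four removals out of 14, and removal of non-responders from one arm only. Balanced removals unrelated to response give zero expected bias. With 14 per arm each participant is 1/14 = 7.1% of the arm, so even a few removals matter.

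**What to change.** - **7.1 and 14.2:** reconcile both with Section 8. State that an event after randomisation may affect treatment, as the clinicians decide, but does not by itself end follow-up. Participants who still consent keep their scheduled visits and the week-12 ulcer measurement and remain in their randomised group. Keep the pre-screening cellulitis row as the eligibility check. No change to any clinical rule on treatment is proposed.
- **Trial Summary, analysis timelines:** time the final analysis by the last randomised participant reaching week 12 or withdrawing, since 28 is also the number randomised.

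The cost is wording in three places and continued scheduled visits for the few participants who stop treatment. No additional patients are needed.

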## 7.2 Participant Assessments Pre- Registration

- **Assessment of eligibility** – Full skin assessment and has to undergo 4 weeks of compression bandaging for venous ulcer
- Complete medical history including Smoking History
- **Assessment of concomitant medications** will be performed at baseline, during treatment and at all follow-up points throughout the study.
- **Blood Sample** will be taken to screen for (TB, HEP B, C and HIV).
- **Physical examination (weight, temperature, blood pressure)** will be assessed at baseline and at all follow-up points throughout the study
- **Photograph of the Ulcer** will be measured using standard medical photography and will be measured at baseline and follow-up points throughout the study. The size of the ulcer will be monitored from these images.
- **Skin biopsy (all patients)** will be performed on all patients at Baseline and at 12 weeks. Skin Biopsy will not be performed on a participant that has achieved full wound healing.
- **Swab** a swab will be taken of the ulcer at baseline, 6 weeks and at week 12 of the study.
- **Saliva sample (all patients)** will be taken for all patients at Baseline and 12 weeks.
- **Leg circulation** will be assessed by looking for signs of pitting oedema, leg ulcer or intermittent claudication, lower limb pulse palpation. Leg circulation will be assessed by the clinician at baseline and at all follow-up points throughout the study.
- **DLQI** assessment will be completed by patients at baseline and at 12 weeks.

## 8 DISCONTINUATION / WITHDRAWAL / TRANSFER

A Trial Participant may discontinue trial treatment for any of the following reasons:

- Intercurrent illness which prevents further treatment
- Withdrawal of consent for treatment by participant
- Any alterations in the participant's condition which justifies the discontinuation of treatment in the investigator's opinion
- Non-compliance with the compression bandaging
- Not attending the scheduled follow-up appointments

Discontinuation of treatment does not necessarily indicate withdrawal from the trial. The distinction between discontinuation of treatment and withdrawal from the trial is shown by the definitions in the following subsections.

### 8.1 Protocol Treatment Discontinuation

A participant would be considered to have discontinued treatment where trial related treatment is ceased according to the reason(s) outlined above. The participant may however still agree to further follow-up assessments as scheduled in Section 7.1.

The participants' discontinuation of treatment must be documented in the medical records and transcribed onto the relevant Case Report Form (CRF).

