## 8.2 Withdrawal from Trial

Trial Participants have the option to completely withdraw from the trial at any time without giving a reason. Total withdrawal would occur in the circumstance that the participant decides to completely withdraw from all treatment aspects of the trial and does not agree to any further scheduled follow up assessments. The participants' total withdrawal must be documented in the medical records and transcribed onto the relevant CRF. No further information will be collected from this participant for the purpose of this trial.

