### 9.2 Analysis of the Objective

Primary objective

- To compare the proportion of patients achieving a 40% reduction in wound size at week 12 between Ixekizumab and placebo groups.

Secondary Objective

- To compare the average wound size reduction in treated versus placebo group.
- To compare the number and proportion of patients achieving wound closure.
- To compare in an actuarial survival analysis the time to closure between placebo and treatment group.
- To compare average pain score and reduction in pain score at 12 weeks (Pain score 0-10) between placebo and treatment group.
- To compare average Quality of life (QOL) (measured by DLQI) and improvement in QOL at 12 weeks between placebo and treatment group.
- Compliance with compression will be compared as a patient reported outcome.

\*these biological endpoints will depend on availability of funding

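### Section 8.1 allows but does not require follow-up to week 12 after injections stop, and no DLQI is planned for early leavers, so week-12 ulcer size and all post-baseline DLQI can be lost

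*Protocol*

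**What the plan says.** Section 8 of the protocol lists the reasons for which trial treatment may stop. Besides intercurrent illness, withdrawn consent for treatment and a change in the participant's condition, they include "Non-compliance with the compression bandaging" and "Not attending the scheduled follow-up appointments". The section adds: "Discontinuation of treatment does not necessarily indicate withdrawal from the trial".

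Section 8.1 covers those who stop treatment: "The participant may however still agree to further follow-up assessments as scheduled in Section 7.1". Section 8.2 defines total withdrawal as the participant's own decision to leave all treatment and to decline further scheduled assessments. Only for that group does it state: "No further information will be collected from this participant for the purpose of this trial". Each state is to be recorded in the medical records and on the relevant CRF.

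On measurements, Section 7.2 says that the ulcer photograph, from which size is taken, "will be measured at baseline and follow-up points throughout the study", and the table in Section 7.1 ticks ulcer assessment at every dosing visit. For DLQI, Section 7.2 says that the "assessment will be completed by patients at baseline and at 12 weeks". The 7.1 table agrees, with one tick at pre-screening and one in its last column. Neither section describes an assessment for a participant who leaves early.

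The primary analysis in Section 9.2 is: "To compare the proportion of patients achieving a 40% reduction in wound size at week 12 between Ixekizumab and placebo groups".

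**The concern.** Both the primary responder comparison and the DLQI comparison are fixed at week 12. Whether those values exist for someone who has stopped injections depends on Section 8.1, which permits follow-up without requiring it. A participant stopped for missed visits or poor compression use may have neither agreed to nor refused further assessments, and the protocol does not tell the site to seek the week-12 measurement.

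The listed reasons for stopping are plausibly related to the outcome. Compression is part of the standard care given in both arms (Section 3), so poor use of it may affect healing, and illness or a change in condition may do so too. Loss of this kind could bias the comparison of arms as well as reduce its precision. With 14 patients per arm, a few such losses matter.

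An analysis plan can choose how to handle a missing value, but it cannot recover a measurement that was never taken. What is collected after stopping is a protocol matter.

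**Working it through.** **Is the gap in the text?** Set side by side, the sections give three situations.

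| Situation | Rule in the protocol | Week-12 data |
|---|---|---|
| Stops injections, agrees to follow-up | 8.1: assessed as in 7.1 | Collected |
| Stops injections, refuses all further assessments | 8.2: data collection ends | Lost, by the participant's choice |
| Stops injections, has neither agreed nor refused | Not withdrawn under 8.2; 8.1 permits follow-up | No requirement to obtain them |

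The third row is the gap.

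**What is missing for a participant last seen at week 8?** Ulcer size exists at baseline and at each two-weekly visit to week 8 (7.1, 7.2), and only the later sizes are absent. DLQI exists at baseline only, although the participant was in the clinic every two weeks. The week-12 column heading is not legible in the 7.1 table as read; the last column is taken as week 12, in line with 7.2.

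**How much could it matter?** The protocol gives no figure for expected loss, so there is none to reproduce. Section 9.1 plans 28 patients in two equal groups, 28/2 = 14 per arm, with no stated allowance for dropout, and the Trial Summary times the final analysis on all 28 completing. The stated 85% power is not used here.

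Let m patients per arm lack the week-12 size, and let x_T and x_C be the responders observed on ixekizumab and placebo. Over all possible outcomes of the missing patients, the difference in responder proportions among all randomised lies between

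- lower: x_T/14 − (x_C + m)/14
- upper: (x_T + m)/14 − x_C/14

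The width is 2m/14: 14, 29 and 43 points for m = 1, 2 and 3.

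The counts below are assumed; the documents give none.

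| m per arm | Observed | Observed difference | Lower bound | Upper bound |
|---|---|---|---|---|
| 2 | 8/12 vs 3/12 | 42 points | 8/14 − 5/14 = 21 points | 10/14 − 3/14 = 50 points |
| 3 | 7/11 vs 3/11 | 36 points | 7/14 − 6/14 = 7 points | 10/14 − 3/14 = 50 points |

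For m = 2, Fisher's exact two-sided p is 0.10 for the observed 8/12 versus 3/12, 0.45 at the lower bound and 0.02 at the upper bound.

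**The case against.** A reader might infer that the default after stopping injections is no follow-up, or that a site need not ask a participant back. The documents do not support that. Section 8 says that stopping is not necessarily withdrawal, and Section 8.2 ends data collection only for someone who declines further assessments. A participant who has refused nothing is still in the trial, and the permissive sentence in 8.1 can be read as a reminder that follow-up is voluntary. Section 14.2 has participants treated off trial when protocol constraints cannot be met, but it speaks of treatment and does not say that assessments stop. This objection stands: the defect is a missing requirement, not a rule against follow-up.

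It is also true that ulcer size is already measured at every visit attended, and that stopping and withdrawal are already recorded separately on the CRF. Neither needs adding.

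Informative loss is an inference from the list of reasons. The protocol speaks of any alteration in condition, without saying for better or worse. The bounds are extremes on assumed counts, and they apply equally to full withdrawals. In the illustration the observed result is already non-significant (p = 0.10), so much of the fragility comes from having only 28 patients. How much loss the wording of 8.1 adds is unknown.

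Finally, DLQI is a secondary endpoint, and a value taken on leaving is not a week-12 value. For someone who simply stops attending, the last visit is not known to be the last. Both points stand and limit what a leaving assessment can give. It would still supply a post-baseline value for those known to be leaving, where at present there is none.

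**Conclusion.** The point holds as a gap in required data collection. Section 8.1 permits but does not require assessment to week 12 for participants who stop injections and have not refused follow-up, and an early leaver contributes no post-baseline DLQI. For the ulcer, the values after the last attended visit are lost, including the one that the primary endpoint uses.

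The size of the effect cannot be derived from the protocol. The range of 21 to 50 points rests on an assumed 2 missing per arm and assumed responder counts. It shows how sensitive a 14-per-arm comparison is to a few missing outcomes; it does not predict the bias due to this sentence. That the loss would be related to healing is plausible but not established. This is an inexpensive improvement worth making in a small trial with no stated dropout allowance.

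**What to change.** Replace the permissive sentence in Section 8.1 with:

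> Participants who stop injections for any reason continue the scheduled assessments to week 12, including the week-12 ulcer measurement, DLQI, pain score and AEs, unless they withdraw consent to follow-up.

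Add a footnote to the table in Section 7.1:

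> A participant known to be leaving before week 12 completes the DLQI and pain score at that visit, alongside the ulcer measurement already scheduled.

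The change leaves dosing, the reasons for stopping treatment and the right to withdraw as they are. No new CRF field is needed, because Sections 8.1 and 8.2 already have the two states recorded. The measurements are already used in the trial. The cost is two wording changes and a few clinic visits without an injection. Participants who refuse follow-up will still be lost.
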